4.4.2.1.7 Ongoing

Ongoing is derived from the last daily intensity of the solicited period computed as described in [Section 4.4.2.1.1](#) and the maximum intensity during the ongoing period. The Investigator's ongoing flag is not used because the measurement would determine the ongoing status of the reaction. Note: The intensity could be considered None (not a reaction) in the analysis despite being considered a reaction by the Investigator (e.g., fever $> 37.5^{\circ}\text{C}$ but $< 38^{\circ}\text{C}$). If the last daily intensity of the solicited period is at least Grade 1 and maximum intensity on the ongoing period is also at least Grade 1, then the reaction is considered ongoing.

4.4.2.2 Unsolicited Non-serious AEs

4.4.2.2.1 Presence

An observation will be considered an event if it has at least a verbatim term and is not a Grade 0 intensity event. Grade 0 events should be included in the listing “Unsolicited non-serious adverse events not included in the safety analysis.”

4.4.2.2.2 Intensity

Intensity for unsolicited non-serious AEs will be derived according to the following classification: None, Grade 1, Grade 2, Grade 3, or Missing.

If the unsolicited non-serious AE is measurable and its preferred term (PT) is part of the list of solicited reactions, then the measurement is derived based upon and following the same rule as the intensity scales defined in [Section 4.4.2.1.1](#) for that measurable injection site or systemic reaction. Intensity for the other unsolicited non-serious AEs will correspond to the value reported in the CRF.

The maximum intensity corresponds to the highest intensity for a unique term.

4.4.2.2.3 Last Vaccination

Last vaccination before an unsolicited non-serious AE is derived from the visit numbers provided in the clinical database and is calculated as follows:

- If an unsolicited non-serious AE has a non-missing visit number, the visit number should be used to determine the last vaccination before the unsolicited non-serious AE
- If the visit number is missing, then the start date should be used to determine the last vaccination before the unsolicited non-serious AE

4.4.2.2.4 Time of Onset

Time of onset is derived from the start date of the unsolicited non-serious AE provided in the clinical database and the date of last vaccination:

- start date of the unsolicited non-serious AE – date of previous vaccination

The time of onset should be considered as missing only if one or both of the dates are missing or partially missing.

Unsolicited non-serious AEs will be analyzed “Within 30 days,” which corresponds to AEs with a time of onset between D0 and D30 days after vaccination or missing. An AE with missing time of onset will be considered to have occurred just after the vaccination indicated by the visit number, so will be included in these tables.

Note: Unsolicited non-serious AE that occurred before vaccination (negative time of onset) or with a time of onset beyond 30 days, will not be included in analysis; but will be listed separately.

Time of onset will be displayed as follows:

- D0-D3
- D4-D7
- D8-D14
- \geq D15
- Missing

4.4.2.2.5 Duration

Duration is derived from the start and stop dates of the unsolicited non-serious AE provided in the clinical database:

- stop date of unsolicited non-serious AE - start date of unsolicited non-serious AE + 1.

The duration should be considered as missing only if the start and / or stop date of the unsolicited non-serious AE is missing or partially missing.

Duration will be displayed by period as following:

- 1-3 days
- 4-7 days
- 8-14 days
- \geq 15 days
- Missing

4.4.2.3 SAEs

4.4.2.3.1 Last Vaccination

Last vaccination before an SAE is derived from the visit numbers provided in the clinical database and is calculated as follows:

- If an SAE has a non-missing visit number, the visit number should be used to determine the last vaccination before the SAE
- If the visit number is missing, then the start date should be used to determine the last vaccination before the SAE

4.4.2.3.2 Time of Onset

Time of onset will be computed using the same methodology as for unsolicited non-serious AEs described in [Section 4.4.2.2.4](#).

SAEs will be analyzed throughout the study using the following periods:

- Within 30 days
- During the study (i.e., all SAEs that occurred during the study)

An SAE with missing time of onset will be considered to have occurred just after the vaccination indicated by the visit number, so will be included in these tables.

Note: SAEs that occurred before vaccination (negative time of onset) will not be included in analysis, but will be listed separately.

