5.3.1.2 Causality

Missing causality (relationship) for unsolicited non-serious AEs and SAEs will be considered at the time of analysis as related to vaccination.

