5.3.1.5 Start Date and Stop Date

Missing or partially missing start dates for unsolicited AEs will remain missing and not be imputed. If either the start or stop date is missing or partially missing, the time of onset will be considered to be missing. Nevertheless, unsolicited AEs with missing time of onset will be included in analyses according to the visit collected.

Missing or partially missing stop dates for AEs (solicited reactions and unsolicited AEs) will remain missing and not be imputed.

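### A partial start date is never compared with the vaccination date, so an event whose known month or year places it before vaccination or after Day 30 can still be counted in the 30-day table

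*SAP*

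**What the plan says.** **When onset is missing.** SAP 4.4.2.2.4 computes time of onset from the event start date and the vaccination date: "The time of onset should be considered as missing only if one or both of the dates are missing or partially missing". Section 4.4.2.3.2 carries this over to SAEs by pointing back to that section: "Time of onset will be computed using the same methodology as for unsolicited non-serious AEs described in". Section 5.3.1.5 closes off imputation: "Missing or partially missing start dates for unsolicited AEs will remain missing and not be imputed".

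**What happens then.** For non-serious AEs: "An AE with missing time of onset will be considered to have occurred just after the vaccination indicated by the visit number", which puts them in the 30-day tables. SAEs enter their own tables in the same way, under a sentence that begins: "An SAE with missing time of onset will be considered to have occurred just after the vaccination indicated by the visit number, so will be".

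**Which vaccination.** Section 4.4.2.3.1: "If an SAE has a non-missing visit number, the visit number should be used to determine the last vaccination before the SAE". The start date is consulted only when the visit number is absent.

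**How out-of-window events are removed.** Section 4.4.2.3.2: "SAEs that occurred before vaccination (negative time of onset) will not be included in analysis, but will be listed separately". Section 4.4.2.2.4 likewise takes non-serious AEs out of the analysis when onset is negative or later than Day 30. Both removals act on a computed onset.

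**Causality.** Section 5.3.1.2: "Missing causality (relationship) for unsolicited non-serious AEs and SAEs will be considered at the time of analysis as related to vaccination".

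**The concern.** The safeguard against counting events outside the window needs a computed number of days, and a partial date never yields one. The month or year that is known may settle the question, but no section compares it with the vaccination date. Two SAEs with the same onset can therefore be treated in opposite ways, solely because the day was recorded for one and not for the other.

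The pre-vaccination side matters for Groups 3 and 4, who are vaccinated at Visit 2, two years after enrollment, and so have a long stretch of study time before the dose. Stage II safety is described on about 40 subjects per group, where a single event visibly moves a percentage. The late side matters in every vaccinated group, because the last visit may fall up to Day 44 while the unsolicited AE analysis stops at Day 30.

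**Working it through.** The SAP states no figure on this point, so there is nothing to reproduce. The check traces the rule through test dates and then sizes one misplaced event.

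**Case (a): before vaccination.** Take a hypothetical Group 3 subject vaccinated at Visit 2 on 15 June 2021.

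| SAE start date | Visit number | Result under the SAP |
|---|---|---|
| 10 Sep 2020 | 2 | Onset = −278 days: excluded and listed |
| Sep 2020, day unknown | 2 | Onset missing: counted after vaccination |
| Sep 2020, day unknown | 1 | No vaccination at that visit; the SAP states no rule |
| Sep 2020, day unknown | missing | Start date decides; the SAP does not say how to use a partial one |

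The second row is the error. Even the latest possible day, 30 September 2020, lies 31+30+31+31+28+31+30+31+15 = 258 days before vaccination, so no completion of the date is compatible with onset after the dose.

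**How far case (a) reaches.**
- Groups 1 and 2 are vaccinated at Visit 1 (Section 3.2), so they have almost no study time before the dose.
- In Groups 3 and 4, Table 3.4 records non-serious AEs only between Visits 2 and 3. Inactive-phase events are therefore essentially SAEs and AESIs.
- Section 3.2 restricts follow-up of these groups after Visit 1 to SAEs judged related to study procedures. The SAE row of Table 3.4 has SAEs and AESIs reported for the whole study. The number of events exposed depends on which of the two applies.

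**Case (b): after Day 30.** Take a subject vaccinated on 31 May. Day 30 is 30 June, Day 31 is 1 July, and the final visit may be as late as Day 44, which is 14 July. An AE dated only July began on Day 31 or later, yet its onset is missing and it enters the 30-day table. This needs a new calendar month to open within Days 31 to 44, a span of 14 days. For SAEs the reach would be wider if the 6-month collection period in Section 4.3.2.5 applies rather than the 30 days in 4.3.2.3.3.

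**A related inconsistency.** Section 5.3.1.5 also makes onset missing when only the stop date is missing. Section 4.4.2.2.4 uses only the start and vaccination dates. Read literally, 5.3.1.5 would send an ongoing event with a complete start date down the same path.

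**Size of one misplaced SAE.** Inputs: n = 40 planned per group (Section 5.5), assumed all vaccinated; 95% Clopper-Pearson interval (Section 5.1.3).

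Lower limit = Beta⁻¹(0.025; x, n−x+1); upper limit = Beta⁻¹(0.975; x+1, n−x).

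- x = 0: 0/40 = 0%; upper limit = 1 − 0.025^(1/40) = 8.8%; CI 0 to 8.8%.
- x = 1: 1/40 = 2.5%; lower limit = 1 − 0.975^(1/40) = 0.06%; CI 0.06 to 13.2%.
- x = 2: 2/40 = 5.0%; CI 0.6 to 16.9%.

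**The case against.** The strongest reply is that this is a deliberate, conservative convention, stated consistently: no imputation, and when in doubt the event counts as post-vaccination. It works well for truly ambiguous dates, and that part stands. It does not cover a date that is incomplete but not in doubt.

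The second reply is that the situation is rare, and this also largely stands. Start and stop dates are to be recorded for every unsolicited AE, SAEs carry complementary forms, contact in the inactive phase is at least once every three months, and a data review precedes lock. A reader might infer that partial dates are likely over a two-year gap. The SAP gives no rate, and the regular calls may equally make unknown dates less common.

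Three further inferences go beyond the documents:
- **That every SAE or AE with a partial date is affected.** Case (a) needs a Group 3 or 4 SAE filed under Visit 2. A Visit 1 record in those groups points to no vaccination and is not moved into the table.
- **That such events are charged to the vaccine.** They are counted in a post-vaccination table. Relatedness is the investigator's separate assessment and defaults to related only when it is missing.
- **That the SAE rate is the only Stage II safety evidence.** Table 5.2 also gives immediate AEs, solicited reactions, unsolicited AEs, discontinuations and MAAEs for Groups 3 and 4. All of it is descriptive.

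**Conclusion.** The point holds in a narrow form. The rule as written ignores date information that can settle the classification, and it gives a wrong result in cases (a) and (b). It is better described as an incomplete rule than as a contradiction of the pre-vaccination exclusion, because that exclusion is explicitly tied to a negative computed onset.

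The shift from 0% to 2.5% is an illustration. It assumes 40 vaccinated subjects in the group, no other SAE, and one SAE that meets every condition of case (a). Nothing in the SAP says how often that will happen. No hypothesis test is touched; what is at risk is the accuracy of small descriptive safety tables.

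**What to change.** 1. In 4.4.2.2.4 and 4.4.2.3.2, add that when the known part of a start date shows onset before vaccination or after Day 30, the event is classified accordingly. Keep the post-vaccination default for wholly missing dates and for partial dates compatible with Day 0 to Day 30.
2. State that events filed under Visit 1 in Groups 3 and 4 attach to no vaccination.
3. Align 5.3.1.5 with this rule, including its stop-date condition, which does not match 4.4.2.2.4.
4. Reconcile the inactive-phase safety collection described in Section 3.2 with the SAE row of Table 3.4.

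The cost is a sentence or two in each of these sections and a simple date comparison in the programs. No new data are needed, and the conservative treatment of ambiguous dates is kept. It should be settled before the database is relocked for Stage II (Section 5.4).

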4.4.2.3.3 Duration

Duration will be computed using the same methodology as for unsolicited non-serious AEs described in [Section 4.4.2.2.5](#).

4.4.2.4 Medically-Attended Adverse Events

MAAEs that occur within 30 days after vaccination(s) will be collected as unsolicited AEs. Unsolicited non-serious AEs that occur within the unsolicited period (within 30 days after vaccination[s]) and have action taken of “Health care provider contact” will be summarized and presented as MAAEs.

4.4.2.4.1 Last Vaccination

Last vaccination will be derived using the same methodology as used for unsolicited non-serious AEs described in [Section 4.4.2.2.3](#).

4.4.2.4.2 Time of Onset

Time of onset will be computed using the same methodology as used for unsolicited non-serious AEs described in [Section 4.4.2.2.4](#).

MAAEs will be analyzed throughout the study using the following periods:

- Within 30 days after vaccination(s)

An MAAE with missing time of onset will be considered to have occurred just after the vaccination indicated by the visit number, so will be included in the safety analysis tables mentioned above.

4.4.2.4.3 Duration

Duration will be computed using the same methodology as for unsolicited non-serious AEs described in [Section 4.4.2.2.5](#)

4.4.2.5 Other Safety Endpoints

4.4.2.5.1 Pregnancy Testing

A urine human chorionic gonadotropin pregnancy test supplied by Sanofi Pasteur will be used to test females of child-bearing potential for pregnancy prior to vaccination. Subjects will not

participate in the study if the initial pregnancy test was positive. For the purposes of the study, female subjects \geq 60 years of age are defined as not of childbearing potential.

4.4.2.5.2 Action Taken

This information will be summarized as collected, including missing observations. No derivation or imputation will be done.

The action(s) taken by the subject to treat and/or manage any **solicited reactions** will be classified in the CRB using the following list (all applicable items should be checked):

- None
- Medication
- Health care provider contact
- Hospitalized

4.4.2.5.3 Seriousness

This information will be summarized as collected. No derivation or imputation will be done.

4.4.2.5.4 Outcome

This information will be summarized as collected. No derivation or imputation will be done.

4.4.2.5.5 Causality

This information will be summarized as collected. An adverse reaction (AR) is defined as an unsolicited non-serious AE or an SAE considered causally related to the vaccine. Missing causality (relationship) will be handled as described in [Section 5.3.1.2](#).

4.4.2.5.6 AEs Leading to Study Discontinuation

A flag is available in the clinical database for all AEs in order to identify AEs leading to discontinuation.

In general, the items that are counted are:

- Disposition table: A subject who has, on the termination form, the reason for early termination “Serious Adverse Event” or “Other adverse event” checked
- Safety overview table: A subject who has either on the termination form, the reason for early termination “Serious Adverse Event” or “Other adverse event” checked or lists an AE on an AE page (solicited, unsolicited, or SAE) that has “Reaction Leading to Termination” or “Event Leading to Termination” or “Serious Adverse Event Leading to Termination” checked that is at least Grade 1 and is within the time period indicated
- SOC/PT table: An event (solicited, unsolicited, or SAE) that has “Reaction Leading to Termination” or “Event Leading to Termination” or “Serious Adverse Event Leading to Termination” checked that is at least Grade 1 and is within the time period indicated

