4.3.2.3.3 Unsolicited Adverse Events

In addition to recording solicited reactions, subjects will be instructed to record any other medical events that may occur during the 30-day period after vaccination. Space will be provided in the diary card for this purpose.

Information on SAEs will be collected and assessed throughout the study, from inclusion until 30 days after vaccination. Any SAE occurring at any time during the study will be reported by the Investigator in the CRB according to the completion instructions provided by the Sponsor; this includes checking the “Serious” box on the AE CRF and completing the appropriate Safety Complementary Information CRFs. All information concerning the SAE is to be reported either as part of the initial reporting or during follow-up reporting if relevant information became available later (e.g., outcome, medical history, results of investigations, copy of hospitalization reports).

For each unsolicited AE (whether serious or non-serious), the following information is to be recorded:

- Start and stop dates^a
- Intensity of the event:

For measurable unsolicited AEs that are part of the list of solicited reactions, the size of the AE as well as the temperature for fever will be collected and analyzed based on the corresponding scale used for solicited reactions (see [Table 4.1](#) and [Table 4.2](#)).

All other unsolicited AEs will be classified according to the following intensity scale:

- Grade 1: A type of AE that is usually transient and may require only minimal treatment or therapeutic intervention. The event does not generally interfere with usual activities of daily living.
- Grade 2: A type of AE that is usually alleviated with additional therapeutic intervention. The event interferes with usual activities of daily living, causing discomfort but poses no significant or permanent risk of harm to the research participant.

^a The stop date of all related AEs will be actively solicited. For other events, the investigator will provide the stop date when it becomes available. AEs for which no stop date was obtained during the course of the study will be considered as ongoing at the end of the study.

- Grade 3: A type of AE that interrupts usual activities of daily living, or significantly affects clinical status, or may require intensive therapeutic intervention.

- Whether the AE was related to the investigational product (for unsolicited systemic AEs)

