4.4.2.1.3 Presence

Presence is derived from the maximum overall intensity on the period considered:

- None: No presence
- Grade 1, Grade 2, or Grade 3: Presence
- Missing: Missing presence

Subjects with at least one non-missing presence for a specific endpoint will be included in the analysis.

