5.3.1.4 Intensity

For solicited reactions, missing intensities will be handled as described in [Section 4.4.2.1.1](#). For unsolicited non-serious AEs, missing intensities will remain missing and will not be imputed.

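### A flagged unsolicited AE with missing intensity counts as an event in SAP 4.4.2.2.1 but is dropped from the discontinuation SOC/PT table by 4.4.2.5.6

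*SAP*

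**What the plan says.** SAP section 4.4.2.5.6 gives three counting rules for AEs leading to study discontinuation.

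- **Disposition table:** the reason on the termination form decides. There is no grade condition.
- **Safety overview table:** the rule begins "A subject who has either on the termination form, the reason for early termination" and accepts either that route or a flagged event on an AE page "that is at least Grade 1 and is within the time period indicated".
- **SOC/PT table:** a flagged solicited reaction, unsolicited AE or SAE, under the same grade and period condition.

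The rules for intensity and presence stand elsewhere.

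- Section 4.4.2.2.1, unsolicited non-serious AEs: "An observation will be considered an event if it has at least a verbatim term and is not a Grade 0 intensity event".
- Section 4.4.2.2.2: "Intensity for unsolicited non-serious AEs will be derived according to the following classification: None, Grade 1, Grade 2, Grade 3, or Missing".
- Section 5.3.1.4: "For unsolicited non-serious AEs, missing intensities will remain missing and will not be imputed".
- Section 4.4.2.1.3, solicited reactions: "Missing: Missing presence".
- Section 4.3.2.3.3, which lists intensity among the items collected: "For each unsolicited AE (whether serious or non-serious), the following information is to be recorded".

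Section 4.4.2.3 on SAEs contains no presence or intensity derivation.

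**The concern.** Excluding Grade 0 and requiring at least Grade 1 are the same condition only when every event has a grade. They part exactly on missing intensity, which the SAP recognises as a category and chooses not to impute. For unsolicited non-serious AEs the general event rule and the discontinuation rule therefore treat the same record differently.

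The record affected is one that the investigator marked as having ended a subject's participation. Such events are few and closely read, and the SOC/PT table is the one that names them. For missing intensity the rule can only undercount.

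It also runs against how the SAP treats other missing safety items. Missing causality is taken as related (5.3.1.2), and unsolicited AEs and SAEs with missing time of onset stay in the analysis (4.4.2.2.4, 4.4.2.3.2).

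**Working it through.** The SAP gives no figure to reproduce here. The check applies its rules to a flagged event, within the period, whose intensity is missing.

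**Step 1. The conditions.**

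- Event rule, unsolicited non-serious (4.4.2.2.1): verbatim term present and intensity not Grade 0. Missing passes.
- Event rule, solicited (4.4.2.1.3): intensity missing gives presence missing.
- Event rule, SAE: none written in 4.4.2.3.
- Disposition (4.4.2.5.6): termination form checked.
- Overview (4.4.2.5.6): form checked, or flagged event of at least Grade 1 in the period.
- SOC/PT (4.4.2.5.6): flagged event of at least Grade 1 in the period. Missing fails.

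**Step 2. The outcomes for missing intensity.**

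| Event type | Termination form | Event rule | Disposition | Overview | SOC/PT |
|---|---|---|---|---|---|
| Unsolicited non-serious | checked | kept | in | in | out |
| Unsolicited non-serious | not checked | kept | out | out | out |
| Solicited | checked | presence missing | in | in | out |
| Solicited | not checked | presence missing | out | out | out |
| SAE | checked | none written | in | in | out |
| SAE | not checked | none written | out | out | out |

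For graded events the conditions agree: Grade 0 fails both the unsolicited event rule and the SOC/PT rule, and Grade 1 or higher passes both. So:

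- Unsolicited non-serious AEs show a direct conflict. The event is kept by 4.4.2.2.1 and always dropped from SOC/PT. It is dropped from the overview only when the form is not checked.
- Solicited reactions show no conflict, because 4.4.2.1.3 does not count them as present either.
- SAEs show a gap. The filter applies to them, but no SAE event rule says what to do when the grade is blank.

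**Step 3. Size, assuming exactly one such event.** The planned group sizes are in section 5.5: 180 each for Groups 1 and 2, and 40 each for Groups 3 and 4. The intervals are exact Clopper-Pearson 95% limits, the SAP's method for safety proportions. For x = 0 the upper limit is 1 − 0.025^(1/n). For x = 1 the lower limit is 1 − 0.975^(1/n), and the upper limit is the 0.975 quantile of Beta(2, n − 1).

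| n | Present rule | Missing intensity counted |
|---|---|---|
| 180 | 0/180 = 0% (0 to 2.03%) | 1/180 = 0.56% (0.01 to 3.06%) |
| 40 | 0/40 = 0% (0 to 8.81%) | 1/40 = 2.5% (0.06 to 13.16%) |

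These figures show what one dropped event does to an otherwise empty row. They do not say how often it will happen.

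**The case against.** The strongest reply is that the situation hardly arises. It needs an AE that led to withdrawal, was flagged, and still has no grade. Section 5.6 describes a data review with a statistical component before database lock, which is where a blank grade should be found. Section 4.4.2.5.6 introduces its rules as general conventions. The event also stays in the unsolicited AE analysis, and the subject stays in the disposition and overview tables when the form is checked. All of this stands and limits the importance. It does not make the two rules agree, and a query process is no reason to keep a filter that discards whatever it fails to resolve.

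Three stronger readings are tempting, and the SAP does not support them.

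- A reader might infer that discontinuations in general are counted only at Grade 1 or higher. The disposition table and the overview's termination-form route carry no grade condition.
- A reader might infer that SAEs are routinely lost, because intensity is missing from the SAE endpoint in 4.3.2.2 and from the SAE row of Table 5.2. Those places govern what is reported for SAEs. Section 4.3.2.3.3 has intensity recorded for serious events too, and the Table 5.2 row for AEs leading to discontinuation lists intensity. Only an SAE whose grade was left blank is exposed.
- A reader might infer that the grade filter is why the overview and SOC/PT tables can disagree. It is one cause. They differ by construction as well: the overview accepts the termination form alone, whereas SOC/PT needs a flagged event in the period.

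**Conclusion.** The point holds for unsolicited non-serious AEs. Sections 4.4.2.2.1 and 4.4.2.5.6 treat a flagged event with missing intensity differently, and section 5.3.1.4 rules out the imputation that would reconcile them. The result is an omission from the discontinuation SOC/PT table in every such case, and from the safety overview when the termination form is not checked. For SAEs with a blank grade the same omission follows, as an unaddressed case and not a contradiction. Solicited reactions are handled consistently.

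This rests on reading the grade and period condition in the overview bullet as attached to the AE-page route only, which is the natural reading of the sentence. The number of flagged events without a grade is not given in the SAP and is probably very small. Only descriptive safety tables are touched; no hypothesis or decision rule is affected. It is a minor correction worth making.

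**What to change.** In the safety overview bullet (AE-page route) and the SOC/PT bullet of section 4.4.2.5.6, split the grade condition by event type:

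- unsolicited AEs and SAEs: *is not Grade 0; missing intensity is counted and shown as Missing*;
- solicited reactions: keep the present minimum of Grade 1, in line with section 4.4.2.1.3.

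The split matters. Extending the new wording to solicited reactions would count a reaction whose presence section 4.4.2.1.3 treats as missing, and so create a new inconsistency. Naming SAEs in the first line also closes the gap for those without a grade.

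The cost is a few words in the SAP and one programming condition. No new data are needed. The change does not remove the other built-in differences between the overview and SOC/PT tables.
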